2. Cirrhosis or advanced bridging fibrosis wherein the subject has greater than 5 years of obesity (body mass index [BMI] >30) and/or diabetes with negative viral hepatitis markers and a biopsy showing cirrhosis or advanced bridging fibrosis with any amount of fat

Subjects who meet all of the inclusion criteria and none of the exclusion criteria will proceed to randomization and the treatment phase. Subjects who fail to meet eligibility criteria due to an abnormal laboratory result may undergo retesting of the abnormal laboratory parameter during the screening window and at the discretion of the investigator and with prior approval of the medical monitor.

**Treatment Phase:** Subjects with portal hypertension who meet all of the other criteria for study inclusion will be randomly assigned (1:1:1) to receive 1 of 3 treatment assignments including placebo, GR-MD-02 in a dose of 2 mg/kg lean body mass, or GR-MD-02 in a dose of 8 mg/kg lean body mass administered every other week over a 52-week period for a total of 26 infusions. During the treatment phase of the study, all subjects randomly assigned to IMP will attend study visits according to the schedule of visits for study administration and monitoring (Table 12-2). Safety (12-lead electrocardiogram [ECG], physical examinations, vital sign measurements, adverse event [AE] monitoring, and safety laboratory assessments), and efficacy (FibroScan, MBT (if available), biomarkers, assessment of cirrhosis complications [esophageal variceal hemorrhage or portal hypertensive gastropathy

hemorrhage, clinically apparent ascites, spontaneous bacterial peritonitis, overt hepatic encephalopathy, listing for a liver transplant or the performance of a liver transplant], and quality of life) will be monitored throughout the treatment phase.

**Postdose Final Visit (14-28 days):** All subjects will attend a visit (or visits) 14 to 28 days after final dose. During this visit, safety (AE monitoring and safety laboratory assessments) and efficacy (FibroScan, MBT [if available], biomarkers, EGD, HVPG, and a liver biopsy) assessments will be collected/performed ([Table 12-2](#)).

**Follow-up/Early Termination Visit:** All subjects are to attend a follow-up/early termination visit 14 days after the postdose final visit to evaluate safety. During this visit, a 12-lead ECG, a physical examination, vital sign measurements, and AE monitoring will be collected/performed ([Table 12-2](#)).

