### **6.1.3.12 Infusion Visit 26 (Week 51 ± 3 Days)**

The following procedures and assessments will be performed prior to administration of IMP:

- Enter the IWRS and register subject visit data.
- CLDQ (This questionnaire will be given to the subject at the beginning of the visit and will be considered source documentation.)
- Assessment of cirrhosis complications.

- Perform a limited physical examination (including weight and examination of the heart, lung, and abdomen).
- Collect vital sign measurements (including heart and respiratory rate, blood pressure, and body temperature).
- Perform hematology testing.
- Perform blood chemistry testing.
- Obtain MELD score.
- Collect plasma and serum sample for freezing at  $-20^{\circ}\text{C}$ .

The following information will be collected after IMP administration:

- Obtain Child-Turcotte-Pugh score and class (A, B, or C).
- AE monitoring.
- Record concomitant medications.

The following will be collected 2 hours after the end of the IMP infusion:

- Collect PK sample

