#### **6.1.4 Follow-up (14-28 Days After Final Dose; Weeks 53-55 $\pm$ 3 Days)**

Within 14 to 28 days after the final 26th dose of IMP or, where feasible, following study termination, the following information will be collected ([Table 12-2](#)):

- Enter the IWRS and register subject visit data
- Perform a limited physical examination including weight and examination of the heart, lung, and abdomen)
- Collect vital sign measurements (including heart and respiratory rate, blood pressure, and body temperature)

- Conduct a FibroScan
- Perform MBT (if available)
- Collect biomarkers blood sample (will include the ELF test, FibroTest [FibroSure], and galectin-3)
- Perform EGD (must be performed on a different day within the 14 to 28-day follow-up period than when the HVPG assessment is performed)
- Perform HVPG
- Obtain a liver biopsy
- Perform hematology testing
- Perform blood chemistry testing
- AE monitoring
- Record concomitant medications

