### **6.2.7 EGD Evaluation**

Subjects will undergo an EGD within 2 months prior to randomization and within 14 to 28 days after the final 26th dose of IMP or where feasible following study termination and the following information will be collected.

Esophageal varices, if present, will be classified as follows:

1. Large varices >50% impingement on the lumen;
2. Small varices <25% impingement on lumen;
3. Medium varices are intermediate between small and large varices.

Subjects with medium or large varices or varices with red signs, regardless of size, will be excluded from study participation. Red signs include red wale markings (dilated venules oriented longitudinally on the variceal surface), cherry red spots (small, red, spotty dilated venules usually about 2 mm in diameter on the variceal surface) or hematocystic spots (large, round, crimson red projection greater than 3 mm that looks like a blood blister on the variceal surface). Subjects without varices or with small varices will advance to HVPG measurement and liver biopsy. Consistent with the American Association for the Study of Liver Disease practice guidelines ([Garcia-Tsao 2007](#)), subjects with small varices will not receive treatment

with nonselective  $\beta$ -adrenergic inhibitors or variceal ligation therapy during the clinical study since long-term benefit has not been established for small varices. At the discretion of the principal investigator, subjects who have no varices or small varices and are currently on  $\beta$ -adrenergic inhibitors may be withdrawn from therapy at least 4 weeks prior to randomization.

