3.1. Overall Study Design and Plan

This is a Phase 2, multi-center, parallel group, North American, randomized, placebo-controlled, double-blind study of subjects with portal hypertension due to cirrhosis.

Approximately 156 subjects with portal hypertension (HVPG ≥ 6 mm Hg) will be enrolled in the study at 45 to 60 study centers in the US and Canada. The subject must have a liver biopsy showing cirrhosis (Ishak stage 5 or 6) presumably due to NASH, excluding subjects with medium and large varices and those with decompensated cirrhosis (as defined by the presence of clinically detectable ascites, any episode of variceal bleeding, and overt hepatic encephalopathy).

Subjects with portal hypertension and the appropriate biopsy findings will be randomized in a 1:1:1 ratio according to the randomization schedule to receive 1 of 3 treatment assignments: placebo, GR-MD-02 in dose of 2 mg/kg lean body mass (LBM), or GR-MD-02 in a dose of 8 mg/kg LBM administered every other week over a 52 week period for a total of 26 infusions. (Figure 3-1)

The study includes Prescreening, Screening, Treatment, Follow-up phases.

Prescreening: Prescreening may begin at Week -9 to evaluate the eligibility for diagnosis of NASH and FibroScan[®] (at sites where it is available). Subjects with qualifying diagnosis and FibroScan[®] score may proceed to screening.

Screening: The screening window is up to 8 weeks after prescreening visit. Subjects will undergo the following required procedures to assess eligibility during the screening period: EGD, HVPG measurement, liver biopsy, MBT (if available) and serum transaminases. Subjects who meet all of the inclusion criteria and none of the exclusion criteria will proceed to randomization and the treatment phase.

Treatment Phase: Subjects will be randomly assigned (1:1:1) to receive 1 of 3 treatment assignments before the first infusion and will be administered every other week over a 52 week period for a total of 26 infusions. Safety and efficacy assessment will be monitored during the treatment phase.

Medical Care of Cirrhosis During the Study: General care of subjects with cirrhosis will be maintained during the study, including screening for hepatocellular carcinoma, at the discretion of the investigator.

[figure not shown]
Post Final Visit (14-28 Days): All subjects will attend a visit (or visits) 14 to 28 days after final dose. During this visit, selected safety and efficacy assessments will be collected/performed.

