Follow-up/Early Termination Visit: All subjects are to attend a follow-up/early termination visit 14 days after the postdose final visit to evaluate safety. During this visit, safety assessments will be collected/performed. Whenever possible, all subjects who are terminated from the study early should have a FibroScan[®] and an MBT performed at a follow-up visit. Whenever possible, subjects who are terminated from the study following at least 13 infusions should also have all the post-study evaluations including EGD, HVPG, and liver biopsy performed in addition to the FibroScan[®] and MBT.

Open-Label Extension Study: Following study completion, subjects will be offered enrollment into a subsequent separate study, an open-label extension study (OLES), if there is adequate tolerability and no safety issues or signs of clinical progression that would require discontinuation.

End-of-Study Telephone Contact: Subjects who do not enroll into the OLES, will be contacted via phone every 6 months for 2 years, and annually thereafter for a total of 4 years, for a brief update and are to be assessed for survival, listing for liver transplantation, liver transplantation, or complications of chronic liver disease (ascites, spontaneous bacterial peritonitis, variceal bleeding, and encephalopathy).

Figure 3-1 Study Design GT-026

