- Time to complications of cirrhosis will be analyzed using Kaplan-Meier curves and compared between treatment groups using a log-rank test. Median time to

complications of cirrhosis, Q1 and Q3 will be presented, along with 95% CI. Time to complications of cirrhosis is defined as the time from the date of randomization to the first documentation of any complication of cirrhosis described in section 8.2. Subjects without development of complications of cirrhosis will be censored at the date of last assessment of cirrhosis complications.

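### The censoring date for time to complications is undefined in SAP 8.2.1, and on either reading event-free completers leave the risk set too early, so the Kaplan-Meier results are wrong

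*SAP*

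**What the plan says.** SAP 8.2.1 runs the clock from randomization to the "first documentation of any complication of cirrhosis described in section 8.2". The list in SAP 8.2 includes new varices and growth of small varices, as well as clinical events, score thresholds, transplant and liver death. For everyone else, "Subjects without development of complications of cirrhosis will be censored at the date of last assessment of cirrhosis complications". The SAP does not say which visit or procedure supplies that date. It commits to reporting the median and quartiles with confidence intervals, and a log-rank test.

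In the supplied protocol, "Assessment of cirrhosis complications" is a named procedure. It appears in the list for Infusion Visit 26 (Week 51, section 6.1.3.12), which is also its last mark in Table 12-2. It is absent from the lists for Weeks 53 to 55 (6.1.4) and Week 57 (6.1.5). The Treatment Phase paragraph of section 3.1 describes its content: "assessment of cirrhosis complications [esophageal variceal hemorrhage or portal hypertensive gastropathy" bleeding, then ascites, peritonitis, encephalopathy and transplant. Endoscopic varices are not mentioned.

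The one scheduled post-baseline endoscopy is done "within 14 to 28 days after the final 26th dose of IMP" (Protocol 6.2.7; also 6.1.4).

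**The concern.** A censoring date must not depend on whether the subject later has the event. If clean completers are censored at Week 51 and positive completers have their event two to four weeks later, being at risk at the time of the EGD depends on the EGD result. The late risk set then contains almost only subjects who are about to have an event. The curve falls towards zero whatever the true incidence, and the log-rank test compares little more than the order of EGD appointments.

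The SAP would then report a median near one year even where well under half of the subjects had a complication. The sensitivity analysis could also appear to contradict the chi-square test purely because of its censoring rule.

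**Working it through.** The plan gives no event rate, power or event count for this analysis, so there is no stated figure to reproduce.

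**Inputs from the documents.** 52 per arm (SAP 4.2); 25% dropout (Protocol 7.6), so 52 × 0.75 = 39 completers per arm; infusion k falls in Week 2k − 1, so Visit 26 is Week 51; the EGD follows 14 to 28 days later, at Weeks 53 to 55.

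**Assumptions, not in the documents.** Clinical events 5% per arm; EGD-detected events, placebo vs drug, 30 vs 10%, 30 vs 5%, 20 vs 5% and 20 vs 10%; dropout 0 or 25%; none or half of those leaving after at least 13 infusions having an EGD; up to 0, 14 or 28 days from randomization to first infusion.

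**Reading 1: censor at Week 51.** Take 39 completers with 12 positive EGDs (about 30%) and 27 clean. The 27 leave at Week 51. The curve is then 11/12 × 10/11 × … × 0/1 = 0 and reaches 0.5 at the sixth event. The true event-free proportion is 27/39 = 0.69. With 12 positives on placebo and 4 on drug, the late risk set is 12 against 4, and every member has an event. If EGD dates are distributed alike in both arms, the expected log-rank difference is about zero.

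**Reading 2: censor at the EGD date.** Suppose the order of EGD dates is unrelated to the result. With k still at risk, the next completer to leave multiplies the curve by (k − 1)/k with probability p, and otherwise leaves it unchanged. With distinct dates, the expected final value is the product over k = 1 to 39 of (1 − p/k). That is 0.26 for p = 0.30 (true value 0.70) and 0.41 for p = 0.20 (true value 0.80). Simulations with EGD events only gave 0.27 to 0.31 and 0.43 to 0.47. They are slightly higher because tied dates count events before censoring.

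**Simulation.** 2,000 trials in each of 16 scenarios. Log-rank rejection at two-sided 0.05:

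| Rule | 30 vs 10, 30 vs 5, 20 vs 5% | 20 vs 10% |
|---|---|---|
| Week 51 censoring | 4–7% | 4–7% |
| EGD-date censoring | 31–75% | 15–20% |
| Common nominal time | 34–82% | 17–21% |
| Chi-square, same data | 35–87% | 18–23% |

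Under Week 51 censoring the curve ends at zero in at least 99.6% of placebo arms and 72 to 99.6% of drug arms. A median, on average at day 371 to 389 (Weeks 53 to 56), is reported in at least 99% of placebo arms and 74 to 100% of drug arms.

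Under EGD-date censoring the final value of the curve is:

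| EGD event rate | EGD-date censoring | Correct value |
|---|---|---|
| 30% | 0.24–0.28 | 0.65–0.67 |
| 20% | 0.39–0.42 | 0.75–0.76 |
| 10% | 0.62–0.64 | 0.85–0.86 |
| 5% | 0.77–0.79 | 0.90 |

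Separate simulations found a spurious median in about 50 to 86% of placebo arms under reading 2, at placebo EGD rates of 20 to 30%. Those with EGD events only (39 completers per arm) put log-rank rejection under reading 1 at 5 to 9%.

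**The case against.** The strongest reply is that Week 51 is not what the SAP means. The preceding sentence defines the event by the SAP 8.2 list, which includes varices, so the last assessment would naturally include the EGD. The bracketed list in Protocol 3.1 covers the treatment phase, when no EGD is scheduled, and it also omits the Child-Turcotte-Pugh, MELD and mortality components. The schedule may have changed too. The supplied protocol is the original, while the SAP follows a later design, for example "The subject must have a liver biopsy showing cirrhosis (Ishak stage 5 or 6) presumably due to NASH", where the protocol also admits stage 4. This stands as a reason not to treat Week 51 as settled. It does not rescue the analysis, because the reading 2 distortion does not depend on the Week 51 row.

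The near-null log-rank result also depends on equal clinical event rates. With clinical events of 15 vs 5% and EGD events of 30 vs 10%, reading 1 rejects about 20 to 25%, and with 20 vs 5% about 35%. Common nominal time gives 77% and 87%, so the loss is smaller but still large. If EGD rates are only 10 vs 5%, every rule rejects 6 to 9% and the log-rank loss is immaterial.

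Some variceal findings do enter before Week 51. SAP 3.1 says that, where possible, "subjects who are terminated from the study following at least 13 infusions should also have all the post-study evaluations including EGD". These keep their information, as do unscheduled endoscopies and clinical events.

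Finally, the reach is small: one sensitivity analysis of the last of six key secondary endpoints. The chi-square test and the MITT and PP incidence analyses are untouched. That limits the priority but does not make the reported curves and medians correct.

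**Conclusion.** The concern holds. The censoring date is undefined, and both plausible readings give wrong figures. Under Week 51 censoring the log-rank test has almost no information on variceal incidence in completers (4 to 9% rejection when clinical events are equal between arms), and the placebo curve almost always ends at zero. Under EGD-date censoring the test keeps most of its power, but the curve overstates the event rate. In one setting (30 vs 10%, 25% dropout, half of eligible dropouts with an EGD, lag up to 28 days) rejection is 6.0% under reading 1, 41.9% under reading 2 and 49.2% with a common nominal time, against 51.4% for chi-square.

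The sizes rest on assumed rates; the mechanism does not. Week 51 rests on the original protocol's schedule. No confirmatory decision depends on this analysis, but its output would mislead if reported as planned.

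**What to change.** In SAP 8.2.1, state the censoring date:

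- Event-free subjects with an end-of-study EGD are censored at that visit. EGD-detected events and EGD-negative censoring at the Week 53 to 55 visit share one nominal time.
- Clinical events, and EGDs after early termination, keep their actual dates.
- Subjects without a final EGD are censored at their last complication assessment.

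An acceptable alternative is to restrict the Kaplan-Meier and log-rank analysis to clinically presenting events and leave EGD findings to the incidence analysis.

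The cost is two or three sentences and no new data. The small downside is that scheduled EGD findings lose their exact documentation date.

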8.3. Exploratory Endpoints

Each of the following exploratory efficacy endpoints will be analyzed analogous to the primary efficacy endpoint, using the ANCOVA model unless otherwise specified. For each endpoint, the baseline value of the endpoint will be used as a continuous covariate in the ANCOVA model.

- Difference in health-related quality of life (using the subject-completed CLDQ) following administration of GR-MD-02 or placebo at 1 year
- Baseline-adjusted change in FibroTest (FibroSure) and ELF score at Infusion Visits 7, 13, 20, and 14-28 days after final infusion
- Changes in liver biopsy staining for α -SMA and galectin-3 in subjects treated with GR-MD-02 or placebo at 1 year will be evaluated using robust regression (M estimation method)

CLDQ

CLDQ is a self-administered questionnaire that consists 29 items on a seven-point scale, ranging from the worst (1) to the best (7) possible function. The questionnaire includes following 6 domains:

Domains	Items
Abdominal symptoms (AS)	1, 5, 17
Fatigue (FA)	2, 4, 8, 11, 13
Systemic symptoms (SS)	3, 6, 21, 23, 27
Activity (AC)	7, 9, 14
Emotional function (EF)	10, 12, 15, 16, 19, 20, 24, 26
Worry (WO)	18, 22, 25, 28, 29

Average score of each domain will be computed. The average score across six domain average scores will also be derived as the overall average score. The derived domain average and overall average score will be summarized at scheduled visits. If the score is missing for some individual items, the domain average score should be calculated as an average of available items if more than 50% of items in that domain are available. If 50% or less of the items are available for a domain, the domain average score is set as missing too.

FibroTest (FibroSure) and ELF Score

Missing values will be imputed using the LOCF method for the post-baseline visits for FibroTest score and ELF score. Also, the ANCOVA model will be conducted for both observed values and LOCF values.

Treatment effects for FibroTest score and ELF score overtime will be estimated using MMRM analysis with the FAS population respectively.

Each exploratory test will also be summarized for the FAS population at all scheduled visits, along with the change from baseline descriptively in summary tables.

9. Safety Analysis

All analysis of safety will be conducted using the Safety set.

9.1. Adverse Events

An adverse event (AE), including serious AE (SAE), is defined as any untoward medical occurrence in a subject enrolled into this study, regardless of its causal relationship to IMP.

A treatment-emergent adverse event (TEAE) is defined as any event which occurs on or after the first double-blind dose date and up to 30 days after the last dose date of the double-blind study drug.

In order to determine a TEAE when the start date of an AE is missing or incomplete, it will be assumed to have occurred after the first infusion of IMP except if an incomplete date indicates that the event started prior to the first infusion.

In the event that only a partial end date (month/year) is available, and the month/year occurs before Day 1 of the study, the AE will not be considered treatment-emergent. However, the partial onset date (month/year) of AE will be handled as follows (where UK, UKN and UKNW indicate unknown or missing Day, Month and Year respectively):

- UK-MMM-YYYY:
 - impute the last day of the month, if the year is less than the first dose year or the year is the same as the first dose year and the month is less than or equal to the first dose month;
 - impute 01-MMM-YYYY, if the year is greater than the first dose year or the year is the same as the first dose year and the month is greater than the first dose month;
 - impute the date of the first dose, if the month and year are the same as the first dose month and year.
- UK-UKN-YYYY:
 - impute 31-DEC-YYYY, if the year is less than the first dose year;

- impute 01-JAN-YYYY, if the year is greater than the first dose year;
- impute the date of the first dose, if the year are the same as the first dose year.
- UK-UKN-UKNW: impute date of the first dose.

If the AE end date is complete and the partial AE start date imputed by the rules above is after the AE end date, then the start date will be imputed by the AE end date.

All AEs will be coded according to the most recent version of the Medical Dictionary for Regulatory Activities (MedDRA), version 18.0. Severity of AE will also be reported according to the NCI Common Terminology Criteria for Adverse Events version 4.03.

The incidence of AEs will be summarized in tables with count and percentage of subjects with AEs by system organ class (SOC) and preferred term. Unless otherwise specified, at each level of SOC or preferred term, a subject with multiple events will only be counted once per SOC or preferred term. Percentages of subjects with AEs will be calculated out of the number of subjects in the safety population. Tables will be sorted by SOC and preferred term based on total frequency in overall group.

The following categories of AE will be summarized:

- TEAEs
- Severity (1, 2, 3, 4 and 5) of AEs
- Relationship of AEs to study drug
- Grade 3 or greater AEs
- AEs leading to discontinuation of study treatment
- AEs leading to death
- Relationship of TEAEs to study drug
- Grade 3 or greater TEAEs
- TEAEs leading to discontinuation of study treatment
- TEAEs leading to death
- SAEs
- Serious TEAEs
- Serious and grade 3 or greater TEAEs
- Serious TEAEs leading to discontinuation of study treatment
- Serious TEAEs leading to death

All AEs will be presented in data listings. TEAEs will be flagged in the listings.

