**Statistical Methods:**

All efficacy and safety parameters, subject demographics as well as medical and social history, and other baseline subject characteristics (including prior NASH treatments and associated response/side effects) will be summarized by treatment group for the 3 individual treatment groups, for both GR-MD-02 treatment groups combined versus the placebo group, for the full-analysis (intent-to-treat), modified intent-to-treat, and per-protocol sets.

Baseline is defined as the last assessment prior to infusion with IMP (ie, the predosing assessment present in the database that is most proximate to the time of IMP administration). Measurements that are obtained after the first dose of study treatment will be considered postbaseline values. Change from baseline is defined as the postbaseline value minus the baseline value.

The primary efficacy endpoint analysis will be carried out using an analysis of covariance model, with the HVPG change from baseline at Weeks 53 to 55 as the dependent variable. The model will include treatment group at randomization and the baseline HVPG as a covariate.

Methods for dealing with missing data including dates, efficacy and safety results will be specified in the statistical analysis plan.

Adverse events will be classified using the Medical Dictionary for Regulatory Activities (MedDRA) (Version 17.1), and summarized by MedDRA system organ class and preferred term. Events from the time of the subject signing informed consent must be reported. Adverse events prior to exposure to IMP are considered pretreatment AEs and will be provided in a listing separate from the listing for TEAEs.

Only TEAEs, and not pretreatment AEs, will be used for tabular summaries and be graded according to the protocol guidelines. Each AE will be assessed for relatedness to the IMP agent per se and for the rest of the infusion procedure. The duration of all TEAEs in days, from start to end, will be summarized as a numeric variable.

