### **6.1.5 Follow-up/Early Termination (Week 57 ± 3 Days)**

Fourteen days after the previous visit ([Section 6.1.4](#)), the following information will be collected ([Table 12-2](#)):

- Enter the IWRS and register subject visit data
- Perform a 12-lead ECG assessment
- Perform a limited physical examination (including weight and examination of the heart, lung, and abdomen)
- Collect vital sign measurements (including heart and respiratory rate, blood pressure, and body temperature)
- AE monitoring

- Record concomitant medications

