### **6.4.5 Adverse Events**

#### **6.4.5.1 Definitions of Adverse Events**

The investigator is responsible for reporting all treatment-emergent AEs (TEAEs) that are observed or reported during the study, regardless of their relationship to IMP or their clinical significance.

An AE is defined as any untoward medical occurrence in a subject enrolled into this study, regardless of its causal relationship to IMP. Subjects will be instructed to contact the investigator at any time after randomization if any symptoms develop.

A TEAE is defined as any event not present before exposure to IMP or any event already present that worsens in either intensity or frequency after exposure to IMP.

An SAE is defined as any event that results in death, is immediately life threatening, requires inpatient hospitalization or prolongation of existing hospitalization, results in persistent or significant disability/incapacity, or is a congenital anomaly/birth defect. Important medical events that may not result in death, be life threatening, or require hospitalization may be considered SAEs when, based upon appropriate medical judgment, they may jeopardize the subject or may require medical or surgical intervention to prevent one of the outcomes listed in this definition. Examples of such medical events include allergic bronchospasm requiring

intensive treatment in an emergency room or at home, blood dyscrasias or convulsions that do not result in inpatient hospitalization, or the development of drug dependency or drug abuse.

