#### **6.4.5.2 Eliciting and Documenting Adverse Events**

All AEs (serious and nonserious) will be assessed beginning at screening and up to 42 days after the last dose of IMP.

Serious AEs that occur more than 42 days after the last dose of IMP need not be reported unless the investigator considers them related to IMP.

At every study visit, subjects will be asked a standard nonleading question to elicit any medically related changes in their well-being. They will also be asked if they have been hospitalized, had any accidents, used any new medications, or changed concomitant medication regimens (both prescription and over-the-counter medications).

In addition to subject observations, AEs identified from any study data (eg, laboratory values, physical examination findings, ECG changes) or identified from review of other documents that are relevant to subject safety will be documented on the AE page in the eCRF.

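### The SAP ends the TEAE window 30 days after the last dose and omits worsening, so events starting on days 31 to 42 are collected but left out of every TEAE table

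*SAP*

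**What the plan says.** **Protocol.** Section 6.4.5.1 states: "A TEAE is defined as any event not present before exposure to IMP or any event already present that worsens" in intensity or frequency after exposure. It sets no upper time limit. Section 6.4.5.2 sets the collection period: "All AEs (serious and nonserious) will be assessed beginning at screening and up to 42 days after the last dose of IMP". The Synopsis (Statistical Methods) says which events are tabulated: "Only TEAEs, and not pretreatment AEs, will be used for tabular summaries". The only events it sets apart are those before exposure.

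**SAP.** Section 9.1 defines a TEAE as an event on or after the first double-blind dose and "up to 30 days after the last dose date of the double-blind study drug". It gives no reason for 30 days and does not mention worsening of an existing event. It then lists two families of tables. One covers TEAEs (all, related, grade 3 or greater, leading to discontinuation, fatal, serious). The other covers AEs and SAEs without the TEAE restriction. All AEs are listed with TEAEs flagged.

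**Visits after the last dose.** Protocol 3.1: "All subjects will attend a visit (or visits) 14 to 28 days after final dose". Then: "All subjects are to attend a follow-up/early termination visit 14 days after the postdose final visit to evaluate safety". SAP 3.1 keeps both visits. Protocol 6.1.5 labels the second one Week 57.

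**The concern.** The two documents classify the same event differently. An AE that starts on day 35 after the last infusion is treatment-emergent under the protocol and belongs in its tables. Under the SAP it is not treatment-emergent. An event present before dosing that becomes worse on treatment meets the protocol definition, but the SAP definition does not name it.

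At stake is the main by-arm safety display. Every TEAE table inherits the cut, including the serious, fatal and grade 3 or greater ones. The excluded days come after the end-of-study HVPG, liver biopsy and EGD (protocol 6.1.4), and for most subjects they include the final safety visit, which has the only ECG scheduled after the last infusion (protocol Table 12-2).

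**Working it through.** **1. Reproduce the protocol's 42 days.** The last infusion is Infusion Visit 26 at Week 51 (protocol 6.1.3.12). The first postdose visit is on day 14 to 28, and the final visit is 14 days after it.

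- Latest final visit: 28 + 14 = 42 days.
- By nominal weeks: (57 − 51) × 7 = 42 days.
- Synopsis postdosing period: 6 weeks × 7 = 42 days.

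All three agree with protocol 6.4.5.2 and with the end of each subject's participation in protocol 4.2.

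**2. Days outside the SAP window.**

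- Excluded onset days: 42 − 30 = 12 (days 31 to 42).
- Share of post-dose collection: 12 / 42 = 28.6%.
- Last infusion day with 26 infusions every 14 days: 25 × 14 + 1 = day 351. Day 42 after it is day 351 + 42 = 393.
- Share of the time from first infusion: 12 / 393 = 3.1%.

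**3. Where the final visit falls.** If the first postdose visit is on day v, the final visit is on day v + 14. The table counts how many of the 14 days between the two visits lie after day 30.

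| First postdose visit (day) | Final visit (day) | Days after day 30, of 14 |
|---|---|---|
| 14 to 16 | 28 to 30 | 0 |
| 17 | 31 | 1 (7%) |
| 21 | 35 | 5 (36%) |
| 28 | 42 | 12 (86%) |

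The final visit is after day 30 for 12 of the 15 permitted first-visit days (17 to 28). Under the nominal Week 57 ± 3 days label it is on day 39 to 45, always after day 30. The SAP limit applies to when the event occurs, not to the visit at which it is reported. An event that starts by day 30 and is first reported at the final visit stays in the TEAE tables.

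**4. Where a day-35 event appears.**

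- TEAE tables in SAP 9.1: no.
- AE tables without the TEAE restriction (severity, relationship, grade 3 or greater, discontinuation, death) and the SAE table: yes, where it meets the category. These tables have no lower time limit, and AEs are collected from screening, when subjects also undergo EGD, HVPG and biopsy (protocol 6.1.2).
- Listings: yes, without the TEAE flag.

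No table in SAP 9.1 covers events from first exposure through day 42 and nothing else.

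**5. Number of events.** The documents give no AE rate. For illustration only, assume a constant onset rate r per subject-year and 52 subjects per arm, all followed to day 42. Expected onsets in days 31 to 42 are 52 × r × 12 / 365.25.

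- r = 0.5: about 0.9 per arm.
- r = 4: about 6.8 per arm.

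**The case against.** The strongest reply is that little is lost and that a bounded window is a legitimate choice.

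- **The visit is still analysed.** A reader might infer that the final safety visit drops out of the analysis. It does not. The cut is by event date, the visit can fall as early as day 28, and SAP 9.4 to 9.6 summarise vital signs, physical examination and ECG by scheduled visit with no TEAE window. Physical examination and vital signs are also done at the earlier postdose visit. This stands.
- **Late serious events are still tabulated.** A reader might infer that serious, fatal or grade 3 or greater events after day 30 disappear from the tables. They do not, because SAP 9.1 tabulates these categories for all AEs as well. Protocol 7.9.4 likewise asks for grade 3 or greater AEs, SAEs and discontinuations without a TEAE limit. For deaths the pooling matters little, since the safety set contains only dosed subjects (SAP 4.3.4). This stands. For the other categories, late events are mixed with pretreatment events, so the tables are not a substitute.
- **Thirty days may be enough.** The safety endpoint in both documents concerns AEs during treatment, and protocol 2.5 reports measurable drug only through 72 hours after a dose. The SAP does not use this argument. It would not favour 30 days over 42 either, since both are far beyond 72 hours. The one 30-day limit in the protocol's analysis sections (7.7, per-protocol set) concerns efficacy events.
- **Worsening is partly captured.** Protocol 6.4.5.3 requires deterioration of a condition present at screening to be recorded as an AE, and such a record can qualify under the SAP. The rule does not clearly reach an AE that starts between screening and the first infusion and then worsens, if it keeps its first onset date.
- **The documents may be from different stages.** The protocol supplied is dated 20 February 2015, and the SAP contains items that it lacks, such as non-dosing PK visits. A later protocol may have changed the TEAE text. The documents do not show this, and the SAP still keeps the final visit for safety.

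**Conclusion.** The conflict is on the face of the documents. SAP 9.1 is narrower than the protocol definition in two ways: it stops at day 30 without a stated reason, and it leaves out worsening. AEs starting 31 to 42 days after the last dose are collected but enter no TEAE table, and no other SAP table gives the protocol-defined incidence through day 42.

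The size is modest: 29% of the post-dose collection days, but only about 3% of the time from first infusion. Both figures assume all 26 infusions on schedule and follow-up to day 42. The 29% should not be read as a share of safety data or of events. The events lost cannot be counted without an AE rate, and nothing in the documents shows that the omission would favour one arm. No efficacy result or sample-size figure is affected. The change is worth making because it is cheap and removes a contradiction in the main safety display.

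**What to change.** In SAP 9.1, define a TEAE as an event with onset, or with worsening in intensity or frequency, from the first infusion through 42 days after the last infusion. This matches the protocol's definition and its collection period. If the team wants a display closer to treatment, keep a 30-day table as a secondary one.

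If the team prefers 30 days as the main window, the SAP should give the reason and tabulate events with onset on days 31 to 42 separately by arm.

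The cost is one sentence and the matching table programming, with no new data. The downside is small: a few off-drug events, or events related to the end-of-study procedures, enter the TEAE tables in all arms.
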